Appendix 2. ECOG Classification of Performance Status

Score	Definition
0	Fully active, able to carry on all pre-disease performance without restriction.
1	Restricted in physically strenuous activity but ambulatory and able to carry out work of a light or sedentary nature, eg, light house work or office work.
2	Ambulatory and capable of all self-care but unable to carry out any work activities. Up and about more than 50% of waking hours.
3	Capable of only limited self-care, confined to bed or chair more than 50% of waking hours.
4	Completely disabled. Cannot carry on any self-care. Totally confined to bed or chair.
5	Dead.

Appendix 3. Clinical Laboratory Tests

The tests detailed in Table 4 will be performed by the local laboratory. Protocol-specific requirements for inclusion or exclusion of participants are detailed in [Section 4](#) of the protocol. Additional tests may be performed at any time during the study as determined necessary by the investigator or required by local regulations. Investigators must document their review of each laboratory safety report.

Table 4. Protocol Required Safety Laboratory Assessments

Hematology	Clinical Chemistry ¹	Other
Hemoglobin	Creatinine	Pregnancy test (urine or serum) will be performed at the screening visit, on Day 1 of every cycle, at the end of treatment visit, and additionally whenever one menstrual cycle is missed or when potential pregnancy is otherwise suspected.
Platelet count	Alkaline phosphatase	
WBC count	AST, ALT	
Absolute neutrophil count	Total bilirubin	
Absolute lymphocyte count	Calcium (total or ionized)	
Absolute monocyte count	Lactate dehydrogenase	
	Magnesium	
	Potassium	
	Glucose, random	
	Sodium	
	BUN or urea	
	Albumin	

¹ In case of potential cases of Drug-Induced Liver Injury, please also refer to protocol [Section 8.6.2](#) Potential Cases of Drug-Induced Liver Injury.

1. VERSION HISTORY

This Statistical Analysis Plan (SAP) for study A7471064 is based on the protocol dated 01APR2020.

Table 1. Summary of Changes

Version/ Date	Associated Protocol Amendment	Rationale	Specific Changes
1 01 Jun 2020	Original 01 April 2020	N/A	N/A

2. INTRODUCTION

This SAP provides the detailed methodology for summary and statistical analyses of the data collected in Study A7471064. This document may modify the plans outlined in the protocol; however, any major modifications of the primary endpoint definition or its analysis will also be reflected in a protocol amendment.

Any deviations from this analysis plan will be described in the Clinical Study Report.

All summaries and analyses will include all data in the database at the end of study which is defined as 1 year after the last participant first visit date in the study.

2.1. Study Objectives, Endpoints, and Estimands

Objectives	Estimands	Endpoints
<hr/>		
Primary		
• To assess safety and tolerability of dacomitinib	• The primary estimand is the incidence of Adverse Events (AEs) from the time of first dose to 28 days post last dosing date or the date of initiation of a new anticancer therapy, whichever occurs first for all participants who receive at least one dose of dacomitinib, regardless of dosing interruptions or dosing compliance.	• Incidence of AEs
<hr/>		
Secondary		
• To evaluate antitumor activity	• The secondary estimand is the treatment effect of dacomitinib as	• Confirmed ORR and DoR as
<hr/>		

of dacitinib by Objective Response Rate (ORR) and Duration of Response (DoR)	assessed by the investigator from time of first dose (for ORR) or time of first tumor response (for DoR) until disease progression, death or initiation of a new anticancer therapy, whichever occurs first for all participants who receive at least one dose of dacitinib without regard to tolerability or discontinuation from treatment	assessed by the investigator using Response Evaluation Criteria in Solid Tumors (RECIST) version 1.1
--	--	--

2.1.1. Primary Estimand

The primary estimand is the incidence of adverse events from the time of first dose to 28 days post last dosing date or the date prior to initiation of a new anticancer therapy, whichever occurs first for all participants who receive at least one dose of dacitinib, regardless of dosing interruptions or dosing compliance. It includes the following 4 attributes:

- Population: Participants with metastatic Non-Small Cell Lung Cancer (NSCLC) with EGFR exon 19 deletion or exon 21 L858R substitution mutations as defined by the inclusion and exclusion criteria, and who receive at least one dose of dacitinib;
- Variable: Binary indicator of whether any AE occurred at least once;
- Intercurrent event(s): All data after the intercurrent event “initiation of a new anticancer therapy (-1 day)” or “treatment discontinuation (+28 days post last dosing date)” will be excluded. Dosing interruptions or dosing compliance are not considered as intercurrent event for this analysis;
- Population-level summary: Incidence of AEs defined as the number of participants with AEs from the time of first dose to 28 days post last dosing date or the date prior to initiation of a new anticancer therapy, divided by the number of participants in the Population.

2.1.2. Secondary Estimands

A secondary estimand is the treatment effect of dacitinib based on ORR with confirmed response as assessed by the investigator from the time of first dose until disease progression, death or initiation of a new anticancer therapy, whichever occurs first for all participants who receive at least one dose of dacitinib regardless of tolerability or duration on treatment. It includes the following 4 attributes:

- Population: Participants with metastatic NSCLC with EGFR exon 19 deletion or exon 21 L858R substitution mutations as defined by the inclusion and exclusion criteria, and who receive at least one dose of dacitinib;

- Variable: Confirmed objective response according to RECIST v1.1 per investigator, defined as Partial Response (PR) or Complete Response (CR) from the date of first dose until disease progression, death or initiation of a new anticancer therapy, whichever occurs first;
- Intercurrent event: All tumor assessments are considered regardless of gaps in assessments. All data after the intercurrent event “initiation of a new anticancer therapy” will be excluded. Dosing interruptions and dosing compliance are not considered as intercurrent event for this analysis;
- Population-level summary: ORR, ie percentage of participants with confirmed CR or confirmed PR and corresponding 95% confidence interval (CI) based on Wilson’s Score Method.

Another secondary estimand is the treatment effect of dacomitinib based on DoR from the time of first tumor response until disease progression, death or initiation of a new anticancer therapy, whichever occurs first for all participants who receive at least one dose of dacomitinib and who show a confirmed objective response per investigator, regardless of tolerability or duration on treatment. It includes the following 4 attributes:

- Population: Participants with metastatic NSCLC with EGFR exon 19 deletion or exon 21 L858R substitution mutations as defined by the inclusion and exclusion criteria, and who receive at least one dose of dacomitinib and showing a confirmed OR per investigator;
- Variable: DoR;
- Intercurrent event: All data after the intercurrent events “initiation of a new anticancer therapy” or “extended gap in tumor assessment, defined as 2 or more missed tumor assessments prior to disease progression or death” will be excluded. Dosing interruptions and dosing compliance are not considered as intercurrent event for this analysis;
- Population-level summary: Kaplan-Meier Median of DoR and 2-sided 95% CI.

2.1.3. Additional Estimand(s)

Not applicable.

2.2. Study Design

This is a Phase 4, open-label, single arm, multicenter, prospective clinical trial of dacomitinib for the first-line treatment of newly diagnosed adult participants with metastatic NSCLC with EGFR exon 19 deletion or exon 21 L858R substitution mutations. This study will enroll a sufficient number of participants to ensure that 100 participants are treated with dacomitinib.

Participants will continue with the study treatment until disease progression, participant refusal/lost to follow-up, or unacceptable toxicity. At the end of the study, participants who are on treatment and benefiting from dacomitinib treatment will be switched to commercially available dacomitinib if considered appropriate by the investigator, as soon as feasible.

3. ENDPOINTS AND BASELINE VARIABLES: DEFINITIONS AND CONVENTIONS

3.1. Primary Endpoint

The primary endpoint is the incidence of AEs, defined as the number of participants with treatment-emergent adverse events (TEAEs) from the time of first dose to 28 days post last dosing date or the date prior to initiation of a new anticancer therapy, divided by the number of participants in the Safety Set (see [Section 4](#)).

An adverse event is considered treatment-emergent if any of the following apply:

- The event occurs on-treatment (defined in [Section 3.5](#)) and was not seen prior to the start of treatment.
- The event was seen prior to the start of treatment but increased in National Cancer Institute Common Terminology Criteria for Adverse Events (NCI CTCAE) v4.03 grade while on-treatment.

Treatment-emergent adverse events will be characterized by type, frequency, severity (as graded by the investigator according to NCI CTCAE version 4.03 and coded by the Sponsor using Medical Dictionary for Regulatory Activities [MedDRA]), timing, seriousness, and relationship to dacomitinib.

3.2. Secondary Endpoints

3.2.1. Overall Response Rate

Objective response based on investigator assessment is defined as CR or PR according to RECIST v1.1. Both CR and PR must be confirmed by repeat assessments performed no less than 4 weeks after the criteria for response are first met. Participants without a CR or PR or with death prior to first post-baseline assessment, inadequate baseline assessment, new anticancer therapy started prior to first post-baseline assessment, and all post-baseline disease assessments missing will be considered as non-responders.

The Best Overall Response (BOR) is the best response recorded from date of first dose until documented Progressive Disease (PD) or start of new anticancer therapy without regard to tolerability or discontinuation from treatment. Additional details are provided in [Section 6.2.1](#).

The Overall Response Rate (ORR) is defined as the proportion of participants with a BOR characterized as either a CR or PR relative to the Safety Set.

3.2.2. Duration of Response

DoR based on investigator assessment is defined, for participants with a confirmed objective response, as the time from first documentation of objective response (CR or PR per RECIST v1.1, whichever is earlier) to the date of first documentation of PD or death due to any cause, whichever occurs first. The censoring rules for DoR are presented in [Section 6.2.2](#).

3.3. Other Endpoint(s)

Not applicable.

3.4. Baseline Variables

Start and end dates of study treatment:

The date of first dose (start date) of study treatment is the earliest date of non-zero dosing of the study drug.

The date of last dose of study treatment is the latest date of non-zero dosing of the study drug.

Definition of baseline:

No windowing will be applied when defining baseline. Any deviations from the protocol specified window will be documented as protocol deviations. A separate definition of adequate baseline will be provided for antitumor activity endpoints.

For antitumor activity analyses and baseline characteristics associated with tumor assessments, the last assessment prior to date of the first dose of study treatment will serve as the baseline assessment.

For safety (including Eastern Cooperative Oncology Group (ECOG) performance status), the last assessment performed on or prior to date of the first dose of study treatment will serve as the baseline assessment. If there are no observations meeting these criteria, then baseline is considered missing.

Participants who start treatment and discontinue from the study on the same day may have two different sets of data collected on study day 1 (one during study and one in the End of Treatment (EOT) visit. Data reported at the EOT visit are not eligible for baseline selection.

Triplicate electrocardiograms (ECGs) are collected pre-dose; therefore the baseline for each ECG measurement is the average of the pre-dose measurements.

3.5. Safety Endpoints

Safety endpoints will be summarized based on the on-treatment period unless otherwise specified.

On-treatment is defined as the time from the first dose of study treatment through end of study follow-up (ie, 28 days after last dose) or the date prior to initiation of a new anticancer therapy, whichever occurs first. The start of new anticancer therapy after the first dose of study treatment is derived as outlined in [Section 5.2.3](#). Adverse events occurring on the same day as the first dose of study treatment will be considered to have occurred during the on-treatment period. All other assessments which occur on the same day as the first dose of study treatment will be considered baseline assessments (see [Section 3.4](#) for baseline definition).

Safety data collected outside the on-treatment period will be listed but not summarized.

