5.6.1. Prohibited Concomitant Treatments

Concomitant use with a PPI decreases dacomitinib concentrations, which may reduce dacomitinib efficacy. The concomitant use of PPIs with dacomitinib should be avoided. As an alternative to PPIs, use locally-acting antacids or an H₂-receptor antagonist. Dacomitinib should be administered at least 6 hours before or 10 hours after taking an H₂-receptor antagonist.

Concomitant use of dacomitinib increases the concentration of drugs that are CYP2D6 substrates which may increase the risk of toxicities of these drugs. The concomitant use of dacomitinib with CYP2D6 substrates should be avoided as minimal increases in concentration of the CYP2D6 substrate may lead to serious or life-threatening toxicities.

Other Antitumor or Experimental Drugs

No additional systemic antitumor therapy will be permitted while participants are receiving a study therapy.

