8.2. Reporting Period

For SAEs, the active reporting period to Pfizer or its designated representative begins from the time that the participant provides informed consent, which is obtained prior to the participant's participation in the study, ie, prior to undergoing any study-related procedure and/or receiving investigational product, through and including 28 calendar days after the last administration of the investigational product. SAEs occurring to a participant after the active reporting period has ended should be reported to the Sponsor if the investigator becomes aware of them; at a minimum, all SAEs that the investigator believes have at least a reasonable possibility of being related to study drug are to be reported to the Sponsor.

AEs (serious and nonserious) should be recorded on the CRF from the time the participant has taken at least 1 dose of study treatment through the last participant visit.

If a participant begins a new anticancer therapy, the AE recording period for nonserious AEs ends at the time the new treatment is started. SAEs and deaths must be recorded and reported if they occur during the SAE reporting period after the last dose of investigational product, irrespective of any intervening treatment. Note that a switch to a commercially available version of the study intervention is considered as a new anticancer therapy for the purposes of SAE reporting.

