9.6.1. Analysis of Primary Endpoint

The primary endpoint is the incidence of AEs. AEs will be summarized by type, frequency, severity (as graded by the investigator according to NCI CTCAE version 4.03 and coded by the Sponsor using MedDRA), timing, seriousness and relationship to dacomitinib. The focus of AE summaries will be on treatment-emergent AEs, those with initial onset or increasing in severity after the first dose of study medication. The number and percentage of participants who experienced any AE, SAE, treatment-related AE, or treatment-related SAE will be summarized descriptively. AEs leading to death or discontinuation of study treatment, events classified as Grade ≥ 3 , treatment-related events, and SAEs will also be summarized. Detailed information collected for each AE will be listed with a description of the event, duration, whether the AE was serious, intensity, relationship to study treatment, action taken, and clinical outcome.

Study Treatment Exposure

Drug exposure will be summarized using descriptive statistics. The number and percentage of participants with dose reduction, temporary/permanent discontinuations and the corresponding reasons will also be summarized. The number and percentage of participants with dose reductions/modifications and the corresponding reasons will also be summarized.

Laboratory Tests

Laboratory test results will be graded according to NCI CTCAE version 4.03. Data will be summarized by the type of laboratory test. Summary of laboratory abnormalities will be presented by maximum CTCAE Grade. For laboratory tests without an NCI CTCAE grade definition, results will be categorized as normal (within normal ranges), abnormal, or not done. Shift tables will be provided to examine the distribution of laboratory abnormalities.

Vital Signs

Vital signs data will be summarized using descriptive statistics (mean, standard deviation, median, quartiles, minimum, and maximum) of actual values and change from baseline for each nominal visit over time (ie, unscheduled assessments will be excluded).

Electrocardiograms

All ECGs obtained during the study will be evaluated for safety. The triplicate data will be averaged, and all summary statistics and data presentations will use the triplicate averaged data.

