5.2.3. Definition of Start of New Anticancer Therapy

Start date of new anticancer therapy (drug, radiation, surgery) is used to determine the end of the on-treatment period (see [Section 3.5](#)) and for censoring in antitumor activity analyses (see [Section 6.2](#)).

The start date of new anticancer therapy is the earliest date after first dose of dacitinib amongst the following:

- Start date of anticancer drug therapy recorded in the ‘Concomitant Medications’ CRF pages with ‘Category of medication’ = ‘Follow-up Cancer Therapy’;
- Start date of radiation therapy recorded in ‘Radiation Treatment’ CRF pages with ‘Subcategory’ = ‘Curative in intent’;
- Surgery date recorded in ‘Non-drug Treatments’ CRF pages with ‘Category’ = ‘On-study Cancer Surgery’ and ‘Outcome of Procedure’ = ‘Resected’ or ‘Partially Resected’.

When start date of anticancer therapy is missing or partially missing, the imputation rules described in [Section 5.3.2.4](#) should be applied using ‘Concomitant Medications’, ‘Radiation Treatment’, and ‘Non-drug Treatments’ CRF pages.

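### SAEs and fatal events that begin once a new anticancer therapy has started, but within 28 days of last dose, are recorded yet enter no SAE or Grade 5 count; one supplementary table would close the gap (low priority)

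*SAP*

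**What the plan says.** **Collection.** Protocol 8.2 stops the recording of nonserious AEs when a new anticancer therapy begins. SAEs and deaths are treated differently: they must be captured "if they occur during the SAE reporting period after the last dose of investigational product, irrespective of any intervening treatment". The SAE reporting period runs to 28 calendar days after the last dose.

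**Counting.** SAP 3.5 ends the on-treatment period at 28 days after last dose or on the day before new anticancer therapy, whichever is earlier. It then states: "Safety data collected outside the on-treatment period will be listed but not summarized". SAP 3.1 uses the same window for the primary endpoint. SAP 6.1.1 applies it, with the treatment-emergent restriction, to the AE tables, including those for serious, treatment-related serious and Grade 5 events. No exception is stated. The cut comes from the primary estimand in SAP 2.1.1, which drops data after the intercurrent event "initiation of a new anticancer therapy (-1 day)".

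**What triggers the cut.** SAP 5.2.3 says: "Start date of new anticancer therapy (drug, radiation, surgery) is used to determine the end of the on-treatment period". Only follow-up cancer drug therapy, curative-intent radiation, and full or partial resection qualify. The clock starts at first dose, not last dose: "The start date of new anticancer therapy is the earliest date after first dose of" dacomitinib.

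**Where the remaining events can be seen.** Under Protocol 9.6.1, detailed information on "each AE will be listed with a description of the event, duration, whether the AE was serious, intensity, relationship to study treatment", and on action taken and outcome. SAP 6.1.1 flags events that are not treatment-emergent in the listings. SAP 6.5.2.1 tabulates study discontinuation by main reason for the Enrolled Set.

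**The concern.** The collection window and the counting window for serious events differ, and the difference always lowers the count. This is a single-arm safety study run at a regulator's request, with AE incidence as its primary endpoint. Its reported percentages for SAEs, related SAEs and Grade 5 events can be lower than what the sponsor has recorded for the same 28 days, and the tables give no sign of it.

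The trigger is ordinary. Dacomitinib stops at progression or unacceptable toxicity, and another therapy may follow within 28 days. A late effect of dacomitinib, or a fatal event, in that interval is recorded but not counted.

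The gap can also open during dosing. Protocol 5.6.1 says "No additional systemic antitumor therapy will be permitted while participants are receiving a study therapy", which leaves local therapy open. A participant who has curative-intent radiation or a resection and continues dacomitinib is outside the on-treatment period from that day, although still on drug. This is probably rare in metastatic disease.

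**Working it through.** **1. The plan's own figure.** Protocol 9.2 gives a maximum standard error of 0.05 for any AE rate with 100 participants. √(p(1−p)/n) at p = 0.5, n = 100 is √(0.25/100) = 0.05, which agrees. There is no hypothesis test, so no power or alpha to reproduce. The SAP plans no confidence interval for AE rates, so none is offered here.

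**2. The two windows side by side.** Set the last dose as day 0 and the start of new therapy as day t, with t from 1 to 28.

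- SAE and death recording ends on day 28 (Protocol 8.2).
- Counting ends on day t − 1 (SAP 2.1.1, 3.1, 3.5, 6.1.1).
- Recorded but uncounted days run from t to 28, which is 28 − t + 1 = 29 − t days.

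| New therapy on day t | Uncounted days (29 − t) |
|---|---|
| 1 | 28 |
| 14 | 15 |
| 28 | 1 |

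These values of t are illustrations. Protocol 9.1.1 places the cut at the date of initiation itself; if that day were counted, the gap would be one day shorter. The working definition in the SAP is the day before.

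**3. Does another output count these events?** SAP 6.3 and 6.4 (other endpoints, subsets) are not applicable. SAP 6.5.2.1 is not cut at new therapy, and SAP 5.2.4 shows that death is a possible discontinuation reason, so deaths in the gap may appear there. That table covers all enrolled participants and is not an SAE, related-SAE or Grade 5 count. Nonfatal SAEs in the gap appear only in listings.

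**4. Size per participant.** One participant whose only SAE (or related SAE, or Grade 5 event) falls in the gap changes the percentage by 1/100 = 1.0 point. A participant already counted for an earlier event of the same kind changes nothing.

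**5. How many.** The documents give no rate for either component. Assume a share q of participants starts new therapy within 28 days of last dose, and a risk s of an SAE or death in the rest of the window. The expected number with an event in the gap is 100 × q × s, and the chance of at least one is 1 − (1 − qs)^100.

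| Assumed q | Assumed s | Expected per 100 | Chance of at least one |
|---|---|---|---|
| 10% | 2% | 0.2 | 0.18 |
| 20% | 5% | 1.0 | 0.63 |
| 40% | 15% | 6.0 | 0.998 |

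The ranges for q and s are assumptions, not estimates. The results are upper limits on the change in a percentage, because some of these participants would already be counted. They do not cover the on-drug case.

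**The case against.** The strongest reply is that this is a deliberate choice. The cut is prespecified and carried through Protocol 2, 9.1.1 and 9.6 and the matching SAP sections. In a study with no comparator, stopping at the next therapy keeps out events that may belong to another treatment. Nothing in the documents shows that the regulator asked for a wider count. The events are listed with seriousness and relationship, and SAEs reach the sponsor within 24 hours of investigator awareness. All of this stands, and it is why the estimand should not change and why the priority is low. What remains is the missing aggregate count: a reader must build it by hand from listings.

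A reader might infer more, and the documents do not support it:

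- *That serious events are lost, or that the plan contradicts itself.* They are recorded and listed, and the summary rule follows the stated estimand.
- *That deaths in the gap vanish from every table.* The disposition summary may show them.
- *That long stretches of dosing time go uncounted.* SAP 5.2.3, read literally, allows this after local therapy, but nothing suggests it is expected in more than a rare participant.
- *That the fatal outcome of an event with earlier onset is certainly dropped, or certainly kept.* SAP 3.1 works by when the event occurs, SAP 2.1.1 excludes later data, and neither says how a subsequent fatal outcome is handled.

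**Conclusion.** The gap is real, but it is a reporting gap and not an error in the plan. SAEs, related SAEs and Grade 5 events with onset from the day new anticancer therapy starts, through 28 days after last dose, enter no SAE or Grade 5 count. The size is unknown and may be zero: 1 percentage point at n = 100 for each participant whose only such event lies in the gap. Any larger figure rests on assumed rates of early switching and of serious events afterwards. The conclusion assumes that SAP 3.5 and 6.1.1 are applied as written, with no unstated extra table. It is a cheap, low-priority improvement to a study whose purpose is to describe safety.

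**What to change.** Keep the primary estimand and all on-treatment tables. Add one table to SAP 6.1.1, labelled supplementary, for the Safety Set. Count events from first dose through 28 days after last dose regardless of new anticancer therapy, and give the number and percent of participants with:

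- any SAE;
- any related SAE, with events of unknown causality shown separately;
- death, with deaths that the investigator attributes to progression of the malignancy shown separately.

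Add an exception for this table to the last sentence of SAP 3.5.

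**Cost.** One table and one clause, from data that Protocol 8.2 already requires. SAP 2 calls for a protocol amendment only for major changes to the primary endpoint definition or its analysis, and this changes neither.

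**Downsides.** Some added events may be due to the next therapy, and there is no comparator to separate them. SAP 6.1.1 treats unknown causality as related, which could inflate the related-SAE row once another treatment has begun; hence the separate display. Protocol 8.6 records a fatal malignancy as a Grade 5 SAE, so progression deaths will also sit in the any-SAE row, and a footnote should say so.
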